#### **14.2.9. Reporting Adverse Events**

All SAEs will be reported as per [Appendix B](#). All SAEs (related and unrelated) will be recorded from the time informed consent is obtained through 30-days after the last dose of study medication, following the end of treatment exposure. Any SAEs considered possibly or probably related to the investigational product and discovered by the Investigator at any time after the study should be reported. All SAEs must be reported to SCYNEXIS, Inc. within 24-hours of the first awareness of the event. The Investigator must complete, sign and date the SAE pages, verify the accuracy of the information recorded on the SAE pages with the corresponding source documents, and email or send a copy by fax to SCYNEXIS, Inc. as per [Appendix B](#).

Additional follow-up information, if required or available, should all be emailed or faxed to SCYNEXIS, Inc. as per [Appendix B](#) within one business day of receipt and this should be completed on a follow-up SAE form and placed with the original SAE information and kept with the appropriate section of the CRF and/or study file.

The clinical research unit is responsible for notifying the relevant regulatory authorities of certain events. It is the Principal Investigator's responsibility to notify the IRB or IEC of all SAEs that occur at his or her site. Investigators will also be notified of all unexpected, serious, drug-related events (7/15 Day Safety Reports) that occur during the clinical trial. Each site is responsible for notifying its IRB or IEC of these additional SAEs.

## 15. STATISTICS

### 15.1. Analytical Plan

All analyses will be conducted in accordance with this study protocol and a Statistical Analysis Plan (SAP) and Tables, Listings, and Figures (TLF) shells which will be prepared and approved by the sponsor prior to database lock. The study objectives are found in Section 8.

### 15.2. Sample Size Determination

There is no formal power calculation. The N is based on practical aspects of recruitment in this population. A sample size of up to 10 participants to complete the study is selected.

### 15.3. Safety Analyses

All adverse events and other safety evaluations (vital signs and clinical safety laboratory tests) will be listed by participant and tabulated for the total number of participants:

#### All Participants:

All adverse events will be coded using the most recent version of the Medical Dictionary for Regulatory Activities (MedDRA). The treatment emergent adverse events (TEAE) will be summarized by system order class (SOC) and preferred term.

Summary statistics and plots will be generated for other safety parameters, including the absolute values and change from baseline values. Some parameters may need to use log scale. It is expected that both the log scale and back-transformed are needed for reporting. No statistical testing will be performed for the safety analysis.

### 15.4. Pharmacokinetic Analysis

Breast milk will be obtained up to 108 hours post dose and blood samples will be obtained starting pre dose the Day 1 morning dose until 108 hours post first dose of study drug for determination of ibrexafungerp concentrations. Sample time points are as follows:

- Breast Milk: complete expression of milk from both breasts (using a standard electric breast pump) will be obtained at the following timepoints and intervals: pre-dose, 0-2, 2-4, 4-8, 8-12, 12-18, 18-24, 24-36, 36-48, 48-72, and 72-108 hours post first dose of study drug.
- Plasma samples will be obtained at the following timepoints: 0 hours (prior to first dose), and at 2, 6, 8, 12 (prior to second dose), 24, 36, 48, 72, and 108 hours post first dose of study drug for determination of ibrexafungerp in plasma concentrations. The 12-hour samples will be taken prior to the second dose of ibrexafungerp.

The following plasma ibrexafungerp pharmacokinetic parameters: area under the curve (AUC), peak plasma concentration ( $C_{max}$ ), time to peak plasma concentration ( $T_{max}$ ), plasma clearance or apparent oral clearance (CL/F), apparent volume of distribution ( $V_d$ ), and terminal half-life ( $t_{1/2}$ ) for ibrexafungerp following oral administration of the VVC dosage regimen for ibrexafungerp will be determined for both breast milk and plasma concentrations.

The following PK parameters of ibrexafungerp in breastmilk: AUC for the different collection periods,  $C_{av}$  based on AUC derived from collections at different time points; total milk concentration data will be used to calculate  $C_{max}$ ,  $C_{min}$  and  $T_{max}$ .

The daily infant dosage (total drug present in milk and consumed by the infant per day) will be calculated:

- Daily Infant Dosage (mg/day) =  $\Sigma$  (total drug concentration in each milk collection multiplied by the expressed milk volume in each milk collection)

The M/P will be calculated.  $M/P = AUC_{0-24} \text{ milk}/AUC_{0-24} \text{ plasma}$ .

The calculation of M/P should be based on AUC and on multiple time points over 24 hours and not just a single point in time.

The relative infant dose (the percent of the weight-adjusted maternal dosage consumed in breast milk over 24 hours) will be calculated:

- Relative Infant Dose = Infant Dosage (mg/kg/day)/Maternal Dosage (mg/kg/day) multiplied by 100.

Individual participant plasma and breast milk concentrations, actual breast milk and blood sampling dates and times, actual volume of breast milk collected at each time interval, actual dosing information (actual time and date of dosing, and actual dose taken), and PK parameters for individuals and the group will be listed in tabular format. Plasma and breast milk concentrations measured over time will be displayed graphically. Plasma and breast milk concentrations and PK parameters will be summarized using descriptive statistics.

The PK of ibrexafungerp plasma and breastmilk will be assayed using validated LC-MSMS methods.

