New curative approaches are needed, particularly involving agents with fungicidal activity (ie, that are able to kill the fungus) and activity against fluconazole-resistant strains, so that the causative yeasts can be eradicated. A new therapeutic approach with these characteristics would be expected to result in improved short-term and potentially long-term outcomes for this condition.

Ibrexafungerp is the first of the triterpenoid class of  $\beta$ -1,3-D glucan synthase inhibitors. It is a semi-synthetic derivative of the natural product enfumafungin with in vitro and in vivo activity against *Candida* species.

It has the same molecular target as the echinocandins but is structurally distinct and may interact differently at the target due to its activity against echinocandin-resistant strains.

Ibrexafungerp has fungicidal in vitro activity against *Candida* species similar to that observed with the echinocandins. By way of comparison, the azoles are fungistatic, with colony forming unit (CFU) counts that parallel the growth control arm.

In June 2021 the US Food and Drug Administration (FDA) approved Ibrexafungerp ([Brexafemme Label, 2021](#)) for treatment of Vulvovaginal candidiasis.

**Adult Pharmacokinetics Summary:** After oral, single-dose administration, peak plasma ibrexafungerp concentrations occur within approximately 4 to 6 hours post-dose. Plasma concentrations declined from  $C_{max}$  in an approximately monophasic decline, with a harmonic mean terminal half-life ( $t_{1/2}$ ) of ~20 hours. The mean  $AUC_{0-\infty}$  and  $C_{max}$  appeared, in general, to be dose proportional for doses from 10 mg to 1600 mg. Plasma exposures of ibrexafungerp were not altered in participants who were older than 65 years compared to younger participants or in female compared to male participants after single oral dose administration.

Ibrexafungerp elimination is primarily hepatic metabolism; and approximately 1 to 2% of the total dose is excreted by the kidney following administration of a single IV dose.

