## 7.2. Rationale for Trial

The primary purpose of this study is to determine whether ibrexafungerp is excreted in breast milk of lactating women, and if so, to characterize PK in breast milk and plasma; calculate the potential infant exposure if lactating women are treated with ibrexafungerp; and characterize the safety and tolerability in lactating women. Based on 24-hour half-life, it is expected that approximately 15% of ibrexafungerp remains after 72 hours, so the collection period of 0 through 108 hours is considered sufficient to characterize the PK parameters.

Vulvovaginal candidiasis (VVC) is a common genital infection in women caused by *Candida spp.*, primarily *C. albicans* and *C. glabrata*. Several studies have reported that 75% of

women experience at least one episode of VVC during their lifetime and 5 to 10% experience recurrent VVC (rVVC) ([Sobel, 2007](#)).

Based on FDA Lactation Study Guidance ([FDA Guidance, 2019](#)), this drug has expected use in women of reproductive age similar to the marketed drugs that are currently commonly used for the indication of VVC in reproductive aged women.

Consequently, evaluation of products for treatment of lactating women with VVC is of importance.

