## 11.5. Standard Meals (in clinic)

### 11.5.1. Standard Meal

Participants will start to consume a standard meal approximately 30 minutes prior to and finish prior to the administration of the ibrexafungerp dose. The clinical research unit will determine the actual content of the standard meals, the meals should fit into the standard meal definition provided below in [Table 4](#). All participants are expected to consume the same meal with regards to kcal and fat content prior to the AM and PM doses.

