4.5.1 Pharmacokinetic Measurements

For pharmacokinetic (PK) assessments, the concentration of ibrexafungerp will be obtained from the blood sample and breast milk sample.

The blood samples will be obtained at the following timepoints: 0 hours (prior to first dose), and at 2, 6, 8, 12 (prior to second dose), 24, 36, 48, 72 and 108 hours post first dose of study drug for determination of ibrexafungerp concentrations in plasma. The 12-hour samples will be taken prior to the second dose of ibrexafungerp.

In breast milk, complete expression of milk from both breasts (using a standard electric breast pump) will be obtained at the following timepoint and intervals: pre-dose, 0-2, 2-4, 4-8, 8-12, 12-18, 18-24, 24-36, 36-48, 48-72, and 72-108 hours post first dose of study drug.

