5.7.2 Pharmacokinetic Parameters

Pharmacokinetic parameters will be derived for ibrexafungerp in plasma and in breast milk for participants in the PK population. Pharmacokinetic parameters are defined in [Table 3](#).

Table 3 : Pharmacokinetic Parameters

Parameter	Description
C_{\max}	Maximum concentration in plasma/breast milk
C_{\min}	Minimum concentration in breast milk
C_{av}	Average concentration in breast milk during the dosing

	interval
AUC ₀₋₂₄	Area under the plasma/breast milk concentration-time curve from time zero to 24 hours
M/P	AUC ₀₋₂₄ milk /AUC ₀₋₂₄ plasma
T _{max}	Time to reach maximum plasma/breast milk concentration
AUC _{0-t}	Area under the plasma/breast milk concentration from time zero to t _{last}
AUC _{0-inf}	Area under the plasma/breast milk concentration from time zero extrapolated to infinity
AUC%extrapolated	Percentage of AUC _{0-inf} due to extrapolation from t _{last} to infinity.
K _{el} or λ _z	Elimination rate constant in plasma
t _{1/2}	Elimination half-life in plasma
CL/F	Clearance or apparent oral clearance in plasma
V _d	Apparent volume of distribution in plasma

PK parameters will be presented by participant in data listings and will be summarized by participants in the PK population using descriptive statistics.

The PK parameters of ibrexafungerp will include maximum concentration (C_{max}) following first dose, area under the concentration-time curve (AUC₀₋₂₄) time to maximum concentration (T_{max}) after the first dose, and elimination half-life (t_{1/2}) after the second dose that will be calculated by means of noncompartmental analysis (NCA) using Phoenix WinNonlin Version 8.4 (Certara USA, Inc.). AUC₀₋₂₄ in milk to plasma ratio is of primary interest to the study objectives. In addition, since blood samples and breast milk will be collected to 108 hours, AUC_{0-t} and AUC_{0-inf} will also be calculated and presented.

Elimination rate constants and AUC determination will be based on the linear trapezoidal rule, and actual PK sample times will be used for the PK analyses. The t_{1/2}, if calculated, will use at least 3 time points from the logarithmic terminal phase portion of the concentration time curve. Pharmacokinetic parameters derived with Kel such as t_{1/2} and AUC_{0-inf}, will be listed but excluded from descriptive statistics if R² _adjusted < 0.8 in λz (Kel) estimation.

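### No plasma sample is drawn between the second dose (12 h) and 24 h, so the planned linear trapezoid understates plasma AUC0-24; the net effect on the milk/plasma ratio cannot be fixed from the documents

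*Protocol*

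**What the plan says.** Plasma is sampled before the first dose and then at "2, 6, 8, 12 (prior to second dose), 24, 36, 48, 72, and 108 hours post first dose of study drug" (Protocol 15.4, repeated in the Synopsis, the Table 5 footnotes and SAP 4.5.1). The 12 h sample is a trough: "The 12-hour samples will be taken prior to the second dose of ibrexafungerp" (SAP 4.5.1). Milk is collected at "pre-dose, 0-2, 2-4, 4-8, 8-12, 12-18, 18-24, 24-36, 36-48, 48-72, and 72-108 hours post first dose of study drug" (SAP 4.5.1), so two collections cover the 12 h in which plasma has no sample before the 24 h draw.

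On method, SAP 5.7.2 states that "AUC determination will be based on the linear trapezoidal rule, and actual PK sample times will be used for the PK analyses". M/P is AUC0-24 in milk divided by AUC0-24 in plasma. SAP 5.7.2 calls this ratio of primary interest, although SAP 3.1 and 3.2 do not list it as an endpoint. Plasma AUC and CL/F, and milk AUC and Cav, are listed primary endpoints (SAP 3.1).

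On kinetics, Protocol 7.1 says that "peak plasma ibrexafungerp concentrations occur within approximately 4 to 6 hours post-dose", with a roughly monophasic decline and a half-life of about 20 h. Protocol 7.2 uses 24 h.

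Neither document mentions the 12 to 24 h gap or corrects for it.

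**The concern.** The second dose contributes a full absorption phase and peak inside the AUC0-24 window, and no plasma sample sees it. A straight line from a pre-dose trough to a point 12 h after dosing lies below the curve throughout. The resulting bias comes from the sampling times, so it is the same with 5 participants or 10. Because the interim is a full SAP analysis and the study may stop there, biased values of AUC0-24 and CL/F could become the final ones.

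M/P adds a second difficulty. Its numerator and denominator cover the second dose differently, and the documents do not settle how the numerator is formed. Recorded expression times (Protocol 13.2), a 5-minute window either side for milk (Protocol Appendix A) and the use of actual times (SAP 5.7.2) point to a trapezoid at the time of pumping. SAP 5.7.2 also asks for milk AUC by collection period. Neither document says how a sample that represents an interval enters a trapezoid.

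**Working it through.** The plan gives no figure for AUC accuracy. Its one related figure is "Based on 24-hour half-life, it is expected that approximately 15% of ibrexafungerp remains after 72 hours". A 24 h half-life leaves 0.5^(72/24) = 12.5% of a dose given at 0 h and 0.5^(60/24) = 17.7% of one given at 12 h. The average is 15.1%, so the figure is consistent with two doses.

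**Inputs.** From the documents: equal doses at 0 and 12 h; Tmax 4, 5 or 6 h; half-life 20 or 24 h; samples at 0, 2, 6, 8, 12, 24, 36, 48, 72 and 108 h. Assumed here: one compartment, first-order or zero-order absorption, lag 0 or 1 h. That gives 3 x 2 x 2 x 2 = 24 scenarios.

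**Worked case** (first-order, half-life 20 h, Tmax 5 h, no lag; concentration scaled so that dose x F / V = 1).

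- ke = ln 2 / 20 = 0.03466 per h. Solving ln(ka/ke)/(ka - ke) = 5 gives ka = 0.6074 per h.
- One dose: c(t) = ka/(ka - ke) x (e^(-ke t) - e^(-ka t)). Two doses: C(t) = c(t) + c(t - 12).
- C at 0, 2, 6, 8, 12 and 24 h: 0, 0.675, 0.834, 0.795, 0.699, 1.161.
- Trapezoid 0-12 h: 0.675 + 3.017 + 1.629 + 2.989 = 8.310. Trapezoid 12-24 h: 12 x (0.699 + 1.161)/2 = 11.157 (from unrounded values). Sum 19.467.
- Exact one-dose area: A(t) = ka/(ka - ke) x [(1 - e^(-ke t))/ke - (1 - e^(-ka t))/ka]. A(12) = 8.667 and A(24) = 15.535. Exact AUC12-24 = A(24) = 15.535; exact AUC0-24 = 24.201.
- Errors: AUC12-24, 11.157/15.535 - 1 = -28.2%. AUC0-24, 19.467/24.201 - 1 = -19.6%. The gap accounts for 18.1 points and coarse sampling before 12 h for 1.5.
- At 16 h the curve is at 1.44, while the straight line is at 0.699 + (4/12) x 0.462 = 0.85.
- AUC0-inf: 54.28 against 2/ke = 57.71, or -5.9%; CL/F is 57.71/54.28 - 1 = +6.3%.

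A linear-up/log-down rule would not help: the 24 h value exceeds the 12 h value, so that segment stays linear.

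**Superposition, same case.** AUC12-24 = AUC0-12 + C(12) x (1 - e^(-12 lambda-z))/lambda-z = 8.310 + 0.699 x (1 - 0.660)/0.03466 = 8.310 + 6.862 = 15.172. AUC0-24 = 8.310 + 15.172 = 23.481 before rounding, an error of -3.0%.

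**Plasma errors over the scenarios**

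| Quantity | First-order | Zero-order |
|---|---|---|
| AUC12-24, linear | -23% to -30% | -18% to -27% |
| AUC0-24, linear | -15.7% to -20.8% | -11.6% to -19.3% |

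Over both models, AUC0-inf is 2% to 7% low, CL/F is 2% to 7% high, and AUC0-24 by superposition is -4.5% to +0.6%. If the second dose peaks 8 to 10 h after it is given, the linear error is about -3% to -15% and superposition errs by +0.4% to +9.5%.

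**M/P error.** The documents give no milk kinetics, so milk delays of 0 to 4 h behind plasma were assumed.

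| Plasma AUC | Milk AUC | Milk concentration is an interval mean | Milk concentration reflects the moment of expression |
|---|---|---|---|
| Linear, as planned | Trapezoid at interval end | -8% to +15% | +10% to +27% |
| Superposition | Trapezoid at interval end | 6% to 19% low | -6% to +9% |
| Superposition | Concentration x interval length | -0.6% to +4.7% | +2% to +24% |

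If the milk AUC were exact and plasma stayed linear, M/P would be 13% to 26% high (worked case: 1/(1 - 0.196) - 1 = +24%).

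**The case against.** The strongest reply is that the size rests on the model. The Tmax in Protocol 7.1 comes from single doses, with no formulation or fed state given for it, and a later peak shrinks the error. That stands: the direction is secure, but 12% to 21% holds only if the second dose peaks at 4 to 6 h.

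The second reply is that superposition assumes the second dose is absorbed like the first. In support, "All participants are expected to consume the same meal with regards to kcal and fat content prior to the AM and PM doses" (Protocol 11.5.1), and exposure appeared "to be dose proportional for doses from 10 mg to 1600 mg" (Protocol 7.1). But later food differs. Under Other Standardized Meals and Restrictions, lunch comes 4 h and a snack 8 h after the morning dose, while the 14 h snack falls 2 h after the second dose. With a much slower second dose, superposition can do worse than the linear rule: in a zero-order case with Tmax going from 6 to 10 h it is 7.3% high against about 6% low. Comparing measured with predicted 24 h concentration need not reveal this. With first-order Tmax going from 5 to 10 h the ratio reads 1.00 while superposition is 5% to 6% high. This also stands, and is why superposition belongs beside the planned value, not in its place.

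Third, consequences are limited: the analysis is descriptive and no threshold rests on AUC or M/P. That is correct. It lowers the weight of the point but does not remove a known bias in a primary endpoint.

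A reader might infer that M/P is therefore overstated by about a quarter, or that milk AUC should be concentration times interval length. The documents support neither. The first needs an accurate milk AUC. The second is a preference over the SAP's actual-time trapezoid, and it does worse if milk reflects the moment of expression.

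**Conclusion.** The planned plasma AUC0-24 is biased low, by about 12% to 21% if the second dose peaks 4 to 6 h after it is given and about 3% to 15% if it peaks at 8 to 10 h. AUC0-inf is about 2% to 7% low and CL/F about 2% to 7% high. These sizes assume one-compartment kinetics, a half-life of 20 to 24 h and the absorption models above.

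The net M/P error has no determined size or sign, because the milk rule is incomplete and the documents do not say whether a milk concentration is an interval mean. The same open rule moves milk Cav (AUC0-24/24 h). Interval-mean concentrations placed at interval end make it 9% to 14% low with no milk delay and 17% to 19% low with a 4 h delay.

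The gap might be read as undermining the infant exposure results. It does not: daily infant dosage and relative infant dose use milk concentration, milk volume and maternal dose, with no plasma term. Whether the drug reaches milk, and milk Cmax and Cmin, are also untouched. This should be fixed, but it does not threaten the study's main question.

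**What to change.** Amend SAP 5.7.2 before the interim soft-lock.

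1. **Plasma.** Keep the planned noncompartmental AUC0-24 and label it as biased low by the 12 to 24 h gap. Beside it, as a sensitivity analysis, report AUC0-24, AUC0-inf, CL/F and M/P with AUC12-24 by superposition: the participant's own 0-12 h profile plus her 12 h concentration decayed with her own lambda-z, or a pooled lambda-z if adjusted R2 is below 0.8. Restrict this to participants who took both full doses. State the assumption of like absorption, that pre-dose meals match but later food does not, and that the 24 h measured/predicted ratio may miss a slow second dose.
2. **Milk.** State one timing rule that fits the SAP's linear trapezoid at actual recorded expression times, and show concentration x actual interval length as a sensitivity analysis. Name neither as preferred. Label every M/P with its plasma method and milk rule, since the pairings err in different directions.

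The cost is a little extra analysis and a second set of AUC and M/P values that rest on a stated assumption. No new procedures are needed. Extra plasma draws between 12 and 24 h for participants still to be enrolled are optional. They would need a protocol amendment and cannot help those already sampled.

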## 15.5. Interim Analysis

An interim analysis will be conducted after five participants have completed their participation in the study. The analysis will involve the examination of pharmacokinetic and safety data and will comprise a full analysis as described in the SAP. The objective of the interim analysis is to determine whether the data from 5 participants is sufficient to address the objectives of the study and fulfill the post marketing requirement (PMR 4069-2); if not the study shall continue to recruit up to 10 participants.

The reporting analysis will involve descriptive statistical methods, including summaries, tabulations, graphs, or by-subject listings. Before initiating this analysis, the data for the study endpoints will undergo a thorough cleaning process, and the database will be soft-locked. The SAP will be finalized before database lock.

## 16. STUDY COMPLETION AND TERMINATION

Study completion is defined as the date the last participant completes the final visit in the study.

Given the unpredictable nature of early Phase 1 studies, it may exceptionally be necessary to keep the study open for gathering/reviewing additional supportive data (preclinical and/or clinical) to optimally complete the objective(s) of the study. In this case, the competent authority

and the ethics committee will be appraised of the maximum extension of the duration of the study beyond the last participant out and the justification for keeping the study open. If necessary, appropriate amendments to the protocol will be generated.

Study termination is defined as a permanent discontinuation of the study due to unanticipated concerns of safety to the study participants or availability of other new data (pharmacokinetic, pharmacodynamic, efficacy, biologic, etc.) arising from clinical or preclinical studies with this study drug. A study may be paused during review of newly available preclinical/clinical safety, pharmacokinetic, pharmacodynamic, efficacy, or biologic data, or other issues of interest or potential concern prior to a final decision for continuation or termination of the study.

